## 1) Background/Justification for Study

Diabetes mellitus is one of the most prevalent chronic diseases in the world and its incidence is expected to increase over the next 20 years. In 2018, approximately 34.2 million Americans (~10%) were affected with the disease. By 2050, the number of Americans diagnosed with diabetes is expected to exceed 48 million. Diabetes mellitus represents a group of metabolic disorders characterized by hyperglycemia and changes in the metabolism of other macronutrients. There are three main types of diabetes mellitus: Type 1, Type 2, and Gestational. Type 1 diabetics are unable to make insulin and are considered insulin-dependent, Type 2 diabetics are insensitive to insulin, and gestational diabetics develop insulin insensitivity, transiently, during or shortly after pregnancy. The etiology of disease may vary between types, yet the resulting pathophysiology is the same: poor peripheral blood flow, decreased cellular response at the injury site, elevated glucose levels, and poor nutrient transport. In addition, due to these mechanisms, some patients develop progressive neurologic dysfunction, called peripheral neuropathy, which affects the most distal nerves first. The late effects of peripheral neuropathy can lead to an insensate foot that is prone to ulceration and subsequent infection.

A common complication of diabetes-induced peripheral neuropathy is the development of diabetic foot ulcers (DFUs). While estimates vary, studies suggest that the average annual incidence of DFUs among diabetic patients may be as high as 6%. DFUs can have a devastating effect on patients' lives, often leading to debilitating injuries, amputations, and even death. It is estimated that foot ulcers are one of the major sources for hospitalization among diabetic patients and precedes up to 84% of lower limb amputations in these patients. In addition to the drastic impact to affected patients, DFUs represent a significant economic burden to the health care system and payers. Estimates place the total cost for management of diabetic foot ulcers between \$9-\$13 billion in addition to treatment and management of diabetes mellitus alone.

Conventional treatment of DFUs including shoe wear modification, self-monitoring, local wound care, brace and shoe offloading, and surgical intervention. More sophisticated treatments including bioengineered cellular technologies and hyperbaric oxygen therapy have been used with limited success. However, these modalities are time consuming, burdensome, costly, and often do not treat the root cause of the problem. Additionally, even with proper care, wounds can take a significantly longer time to heal in diabetic patients. This is due to the altered physiology which does not allow for the proper nutrients and factors to mobilize to the site of injury, leaving wounds at high risk for infection and possible amputation.

In contrast to traditional treatment modalities, nutrition therapy has recently been shown to aide in healing of chronic wounds by providing essential nutrients which were not previously present in necessary amounts. Nutrition therapy has proven useful in modulating inflammation and the immune response, optimizing glucose control, and attenuating the hypermetabolic response to injuries, ultimately improving healing and recovery. Multiple studies have produced strong evidence that nutrition therapy reduces the incidence of complications including poor healing, infections, and development of hypertrophic scars. Thus, supplemental immunonutrition may offer a viable, low cost, rapidly scalable, and widely available approach to enhance the body's ability to heal itself.

Common immunonutrients include arginine, Omega-3 fatty acids, and vitamin C, each of which offer unique properties to enhance self-healing. Arginine is an amino acid that is important for protein metabolism and nitric oxide production; during times of extreme physiologic stress or malnutrition, it is considered an essential amino acid. Studies have suggested that arginine supplementation should be implemented to maintain a proper nitrogen balance for regulation of protein synthesis and to regulate nitric oxide levels for appropriate cellular signaling. Most commonly found in fish, Omega-3 fatty acids, specifically eicosapentaenoic acid (EPA) and docosahexaenoic acid (DHA), are long chain polyunsaturated fats not produced in the human body, making their dietary intake essential. In addition to their well-known cardioprotective effects, Omega-3s compete with arachidonic acid as a substrate for cyclooxygenase and therefore serve as regulators of immune function. Vitamin C is a water-soluble vitamin and a potent antioxidant and has an essential role in collagen biosynthesis. The antioxidant properties of vitamin C help to decrease the release of reactive oxygen and nitrogen species, contributing to the attenuation of a cell's inflammatory state. Vitamin C is also a key cofactor in collagen cross-linking, the process that gives collagen its strength.

Various studies have been conducted with the described nutrients to evaluate their effects in specific patient populations. A multicenter, randomized, controlled, blinded trial evaluated the effect of a nutritional formula enriched with arginine, zinc, and antioxidants in 200 adult malnourished patients with stage 2-4 pressure ulcers. Improved wound healing was observed in patients who received up to 6 grams of arginine daily for 8 weeks compared to the control group. A 2012 study examining various doses of arginine supplementation on wound healing demonstrated that patients with stage 2-4 pressure ulcers receiving either 4.5 or 9 grams of a daily arginine supplement achieved a 2-fold improvement on healing time compared to the control group, illustrating that a lower dose of arginine supplementation is sufficient to elicit clinical benefit. A combination of arginine and vitamin C was shown to be effective for wound healing in a 2005 study involving inpatients with stage 2-4 pressure ulcers. Patients who were randomized to receive a standard diet plus two high-protein/energy supplements containing additional arginine (9 grams), vitamin C (500 mg), and zinc (30 mg) demonstrated a clinically significant improvement in pressure ulcer healing compared to a control group who did not receive the additional supplementation. Additionally, vitamin C (500 mg), in conjunction with vitamin E, has been shown to reverse oxidative stress-induced morphological changes in RBCs, improve anemia, and reduce blood flow to the ulcer area in a randomized trial including 60 adult patients with diabetic foot ulcers following 12 weeks of daily supplementation. The effects of omega-3 fatty acids, specifically 10 grams per day of EPA for 4 weeks, were illustrated in a 2012 study in which patients with pressure ulcers stage 2 or higher were randomized to receive a nutritional formula enriched with fish oil and other antioxidants versus an isonitrogenous nutritional formula. Patients receiving the formula enriched with fish oil and other antioxidants showed decreased progression of pressure ulcers and a decrease in concentrations of C-reactive protein.

While several studies have been conducted on the beneficial effects of L-arginine, omega-3 fatty acids, and vitamin C over a range of subjects and disease conditions, there has yet to be a study involving a combination of these specific nutrients to help better heal chronic wounds in the diabetic population. This study is designed to address this knowledge gap by assessing and comparing the effectiveness of oral immunonutrition versus standard of care wound therapies on diabetic patients, using nutrients that have already been proven to improve wound healing in other

patient populations. If proven to have significant effects, this study will provide an added strategy that may decrease rates of infections, wound complication, amputations, and possibly death in the diabetic population. Additionally, this treatment strategy may decrease resource utilization and cost of care for the treatment of DFUs. Positive results, given the wide availability of these nutrients, would be rapidly translatable, scalable, and deployable in other healthcare centers around the country.

## 2) Objectives / Research Aims

Chronic, non-healing foot ulcers are a common complication of diabetes that can threaten loss of limbs, shorten life expectancy, and require resource-intensive treatment. Patients who exhibit these late effects of diabetes are often medically complex and have not only a shortened life expectancy but also a lower quality of life than their non-ulcer peers. Despite the prevalence of obesity in these patients, many exhibit metabolic signs of malnutrition, malabsorption, or both. Even when direct treatment for the ulcer is ideal, if the patient does not have the metabolic building blocks or the correct macronutrient healing environment, then treatment will be futile.

To this end, we believe focused immunonutrition supplementation consisting of L-Arginine, Omega-3 fatty acids, and Vitamin C combined with quality wound care will lead to an improvement in treatment success, satisfaction, patient reported outcome measures, and limb salvage.

**Specific Aim 1:** To compare the healing process of diabetic patients with chronic, non-healing, lower-extremity wounds receiving oral immunonutrition supplementation to patients receiving traditional care.

- a. This will be addressed by performing a prospective, randomized pilot study including 30 diabetic patients with chronic lower extremity wounds, Wagner stages 1-2. Fifteen patients will receive oral immunonutrition supplementation (2 grams omega-3 fatty acids + 500 mg vitamin C + 4.5 grams L-arginine per day) in addition to current standard of care and 15 patients will receive the current standard of care only. Study participation will continue for 6 weeks.
- b. Effect of wound healing will be assessed utilizing the Pressure Ulcer Scale for Healing (PUSH) Tool 3.0 which scores ulcers based on size ( $\text{cm}^2$ ), exudate amount, and tissue type present. Plantar pressure profiles will be recorded using a Tekscan Pressure Mat and plantar weight-bearing foot images will be recorded. Additionally, patient charts will be monitored over the course of the study to identify rate of infection, surgical intervention, and amputation and for one year following completion of the study to assess ulcer recurrence rates.

**Specific Aim 2:** To assess compliance and patient satisfaction with an oral immunonutrition supplementation regimen in diabetic patients with chronic, non-healing, lower-extremity wounds.

- a. Patients randomized to receive the oral immunonutrition supplementation in addition to standard of care will complete a daily compliance log documenting their intake of the provided supplements.
- b. All patients will complete a weekly survey rating their pain score (VAS) and any symptoms/side effects experienced during their study participation.
- c. At the final visit, subjects randomized to receive the oral immunonutrition supplementation will complete a satisfaction survey in which they detail their thoughts on their treatment plan.

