  - a. If randomized to the control group (SOC only), patients will receive standard of care defined as sharps debridement, appropriate dressing, and offloading. If randomized to the treatment group (SOC + Immunonutrition), subjects will receive standard of care defined as sharps debridement, appropriate dressing, and offloading in addition to a 6-week supply of Omega-3 fatty acids (soft gel form, 2 pills per day, total of 1.68 grams) and L-Arginine/Vitamin C (powder form, to be mixed with 8 oz liquid, 1 scoop once daily, total of 4.5 grams L-arginine and 500 mg vitamin C). Subjects will also be provided a compliance log with detailed instructions for taking and tracking supplements.
5. Patients will be scheduled for biweekly wound checks with their provider (weeks 2, 4, 6). Wound characteristics will be documented at each follow up visit using the PUSH Tool 3.0, images of the wound will be obtained, and an interval history and physical exam will be documented. The provider will verify and document concomitant medications in the patient's chart. The provider will visualize and evaluate any additional wounds that are present (new or present at time of enrollment) and record characteristics in the patient's chart. Patients will complete a questionnaire detailing their pain level (VAS), symptoms experienced during the treatment phase, and any unscheduled visits to emergency departments/urgent care centers. This will be completed via a paper survey in clinic during their office visit (Appendix 4). On weeks where an office visit is not scheduled (weeks 1, 3, 5), a research coordinator will call the patient and collect survey responses (Appendix 3).
6. At the final office visit (week 6), plantar pressure profiles will be recorded via the Tekscan Pressure Mat, and clinical plantar weight-bearing images will be captured. Patients randomized to receive the oral immunonutrition supplementation will complete an additional survey detailing their satisfaction with the treatment plan and any additional thoughts they would like to share (Appendix 5) and return the completed compliance log

(Appendix 6). Patients in the treatment arm will have CMP and lipid panel labs drawn at this timepoint or within 3 months of study completion.

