**Visit 0: Previously scheduled office visit:**

- Provider reviews study with patient, confirms that inclusion/exclusion criteria are met, and obtains informed consent.
- a. Note: If any labs or ECG are required, results will be reviewed by the provider and the patient will resume study activities at their next scheduled visit.
- Provider documents characteristics of wound via PUSH Tool 3.0, obtains plantar pressure profile reading, and captures clinical photos.
- Provider verifies and documents concomitant medications in the patient's chart.
- Provider visualizes and evaluates any additional wounds that are present and records characteristics in the patient's chart.
- Patient is randomized to receive either oral immunonutrition supplementation with standard of care or standard of care alone.
- Patient is provided oral immunonutrition supplements and compliance log, if appropriate.

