**Phone Call 1: (1 Week Call, first call after completing 7 days of oral immunonutrition):**

- Patient completes questionnaire over phone with research coordinator (VAS, experienced symptoms since enrollment, review of supplement compliance).

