## **Appendix 1: Schedule of Events**

### **Visit 0: Previously scheduled office visit**

- Provider reviews study with patient, confirms that inclusion/exclusion criteria are met, and obtains informed consent
  - a. Note: If the patient has not had an ECG (within 3 months of study enrollment), a lipid panel (within 3 months of study enrollment), a CMP/INR/PT (within 3 months of study enrollment), and/or an A1c lab (within 6 months of study enrollment) these will be performed to confirm normal parameters prior to continuation of study activities. If any labs or ECG are required, results will be reviewed by the provider and the patient will resume study activities at their next scheduled visit.
- Provider documents characteristics of wound via PUSH Tool 3.0, obtains plantar pressure profile readings via Tekscan Pressure Mat, and captures clinical photos
- Provider verifies and documents concomitant medications.
- Provider visualizes and evaluates any additional wounds that are present and records characteristics in the patient's chart.
- Patient is randomized to receive either oral immunonutrition supplementation or standard care
- Patient is provided oral immunonutrition supplements and compliance log, if appropriate

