### **Appendix 3: Biweekly Clinic Survey (Weeks 2, 4, 6)**

## **Effects of Supplemental Immunonutrition on Healing of Chronic Non-Healing Lower Extremity Ulcers in Diabetic Patients: Clinic Survey**

Name: \_\_\_\_\_ Date: \_\_\_\_\_

1. Which follow-up visit are you being seen for today?  
 2-week visit  
 4-week visit  
 6-week visit
2. Did you receive immunonutrition supplements (Omega-3 fatty acids, Vitamin C, L-Arginine)?  
 Yes (proceed to question 3) \_\_\_\_\_  
 No (proceed to question 4)
3. Have you experienced any difficulty taking the supplementation according to the instructions?  
 Yes, please explain: \_\_\_\_\_  
 No
4. Have you experienced any of the following symptoms since your surgery? Check all that apply:  

 Abdominal Pain	 Low Blood Pressure
 Heartburn	 Burping
 Nausea	 Taste Perversion
 Vomiting	 Constipation
 Diarrhea	 Gastrointestinal Disorder
 Headache	 Itchy Skin
 Insomnia	 Easy bleeding or bruising
 Rash	 Red, itchy welts
 Indigestion	 Other, please explain: _____
 Palpitations	_____
 Numbness	
 Bitter Taste	
5. Have you made any trips to Emergency Departments/Urgent Care Centers since your last visit related to your foot ulcer?  
 Yes, please explain: \_\_\_\_\_  
 No
6. Circle your current level of pain related to your foot ulcer on the scale below:

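### Pain (VAS) and the symptom checklist are first collected at week 1, so change from before treatment cannot be computed and the checklist alone cannot separate new from pre-existing symptoms

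*Combined protocol and SAP*

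**What the plan says.** Aim 2b in section 2 sets the collection: "All patients will complete a weekly survey rating their pain score (VAS) and any symptoms/side effects experienced during their study participation". The opening of the same section gives the broader expectation that supplementation with wound care "will lead to an improvement in treatment success, satisfaction, patient reported outcome measures, and limb salvage".

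Visit 0 is described in section 6f (numbered procedures and visit list) and in Appendix 1. The visit list reads "Provider documents characteristics of wound via PUSH Tool 3.0, obtains plantar pressure profile reading, and captures clinical photos", followed by concomitant medications, additional wounds, randomisation and supply of supplements. Appendix 1 matches: "Provider documents characteristics of wound via PUSH Tool 3.0, obtains plantar pressure profile readings via Tekscan Pressure Mat, and captures clinical photos". None of these places lists a VAS or a symptom questionnaire.

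The first questionnaire is Phone Call 1, after 7 days of supplement: "Patient completes questionnaire over phone with research coordinator (VAS, experienced symptoms since enrollment, review of supplement compliance". The phone survey then covers the odd weeks: "On weeks where an office visit is not scheduled (weeks 1, 3, 5), a research coordinator will call the patient and collect survey responses". The clinic form in Appendix 3 is titled "Biweekly Clinic Survey (Weeks 2, 4, 6") and offers only those three visits.

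Section 6i lists VAS scores and supplementation side effects among the key data points. Section 6e names neither VAS nor symptoms as a primary, secondary or tertiary outcome. Section 6h gives unadjusted t-tests for continuous measures in general and no model for VAS.

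**The concern.** VAS is the only scored patient-reported measure taken in both arms, because the satisfaction survey goes to the supplement arm only. PUSH and plantar pressure each have a Visit 0 value; pain does not. Without one, nobody can say how far a patient's pain moved from before treatment, whether the arms started alike, or how much noise adjustment would have removed.

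The symptom checklist raises the more serious issue. Numbness is on it and is listed in section 7 as a possible L-arginine effect. The background section describes neuropathy in this population: "The late effects of peripheral neuropathy can lead to an insensate foot that is prone to ulceration and subsequent infection". Constipation, insomnia and low blood pressure are also on the list and can also predate entry. Neither form asks whether a symptom was there before enrolment or has got worse. Section 7 says the risks of the combination are unknown, and the Data Safety Committee reviews events after every 5 enrolled patients. At the first review only a few patients will have been treated, so the control arm gives little background rate and each case has to be judged largely by itself.

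The trial has no placebo. Answers taken before randomisation are the only ones that knowledge of the assignment cannot affect, and they cannot be recovered once dosing starts.

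**Working it through.** **Schedule check.** Every planned contact, side by side:

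| Contact | VAS and symptom checklist |
|---|---|
| Visit 0 (section 6f, Appendix 1) | not listed |
| Week 1, 3, 5 calls (Appendix 4) | yes |
| Week 2, 4, 6 visits (Appendix 3) | yes |

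Appendix 1 mentions visit 0 in its biweekly-visit list only for the pressure reading. Schedule, appendix and forms agree, so this is not a gap from text extraction.

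**Symptom window.** The visit schedule asks about symptoms since enrolment, and the phone form about symptoms during participation. The clinic form dates them from the patient's surgery, which is not an entry event in this trial. None of these excludes a chronic symptom that simply continues.

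**Scale of the pain loss.** The plan states no figure to reproduce. Inputs: 15 per arm (section 6c). Assumed: results in SD units, baseline/follow-up correlation r of 0.3 to 0.7, two-sided alpha 0.05, normal approximation.

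- SE of a difference in means = SD × √(2/15) = 0.365 SD.
- Adjusted SE = 0.365 × √(1 − r²), so the variance falls by r².
- Difference detectable with 80% power = (1.960 + 0.842) × SE.

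| r | Variance cut (r²) | SE (SD) | Detectable difference (SD) | Power for 0.8 SD |
|---|---|---|---|---|
| no baseline | 0 | 0.365 | 1.02 | 59% |
| 0.3 | 9% | 0.348 | 0.98 | 63% |
| 0.5 | 25% | 0.316 | 0.89 | 72% |
| 0.7 | 49% | 0.261 | 0.73 | 87% |

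The formula treats the slope on baseline as known. Estimating it from 30 patients gives back a little of the gain, which matters most at r = 0.3.

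**Unseen imbalance.** P(|difference in baseline means| > d) = 2 × [1 − Φ(d/0.365)]. For d = 0.25 SD this is 49%; for d = 0.5 SD it is 17%.

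**Background symptoms.** Suppose a checklist symptom already affects a proportion p of patients in both arms and treatment does nothing. The expected number of reporters per arm is 15p. The chance that the arms differ by 3 or more comes from two independent Binomial(15, p) counts. The values of p are assumed.

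| p | Expected reporters per arm | P(arms differ by 3 or more) |
|---|---|---|
| 10% | 1.5 | 12% |
| 30% | 4.5 | 32% |
| 50% | 7.5 | 36% |

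These are chance differences, equally likely in either direction. Without a baseline answer, the checklist cannot show which reporters had the symptom at entry.

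**The case against.** A reader might infer that improvement in pain cannot be measured at all, or that a chance baseline difference would bias the result. The documents do not support either reading. VAS is taken weekly in both arms, so the randomised comparison at each week is valid and its standard error already contains chance imbalance. Change from week 1 to week 6 can also be computed. The loss is change from before treatment, the ability to see or adjust for imbalance, and precision.

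A reader might also infer that long-standing symptoms will be counted as effects of the supplement. No section says that checklist ticks are treated as treatment-emergent events. Controls answer the same list, so background symptoms raise the counts in both arms and do not by themselves bias the contrast. Medical history, comorbidities, Visit 0 medications, interval history and examination, and chart review all give some context, and adverse events are graded by CTCAE. This stands as a limit on the point. It does not remove it, because none of these sources is a matched pre-treatment answer to the same items.

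Two further points stand. VAS is not a named endpoint, and the statement about patient-reported outcomes in section 2 does not define a change from baseline. The precision gain may also be small: at r = 0.3 it is 9%, and if many patients have insensate feet, scores could cluster near zero.

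**Conclusion.** The point holds in limited form and should be acted on. As written, the plan permanently loses the pre-treatment VAS and symptom answers, although Visit 0 already takes place before randomisation.

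For pain, the cost is one of precision and description: a variance reduction forgone of about 9% to 49%, resting wholly on an assumed correlation of 0.3 to 0.7. For symptoms, new and pre-existing complaints cannot be separated from the checklist alone. This is the stronger half, because it bears on judging individual adverse events at small-number safety reviews of an unstudied combination. The size of that effect depends on symptom prevalence at entry, which no document gives.

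The consequences are confined to Aim 2b, the patient-reported outcome expectation and the safety data. The primary and secondary wound-closure outcomes are not touched.

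**What to change.** 1. **Visit 0 (section 6f and Appendix 1).** After consent and before randomisation, collect the VAS as current pain, in the same wording as at follow-up. Give the symptom checklist with a stated look-back window before enrolment. The look-back applies to the checklist only; both follow-up forms ask about pain now, so a VAS with a recall period would not match them.
2. **Survey forms (Appendices 3 and 4).** Add a baseline option to the clinic form. Replace its reference to surgery with enrolment. Add to both forms a field for each reported symptom: new, worse than at Visit 0, or unchanged. Neither form can record worsening at present. Section 6f also cites these two appendices the wrong way round, which can be corrected in the same edit.
3. **Analysis (section 6h).** Analyse weekly VAS adjusted for the Visit 0 score. Report all symptoms by arm, with new or worsened ones shown separately from those that were present at Visit 0 and unchanged.

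The cost is a few minutes per patient at a visit already taking place, minor form revisions, and a short addition to the analysis section. No extra visit or procedure is needed.
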